6.11. Efficacy Analyses

6.11.1. Primary Outcome and Methodology

Rate of clinical remission at Week 12 is the primary efficacy outcome for this study and will be analyzed using the ITT population.

The primary objective of this study is to test the hypothesis that treatment with LY3074828 is superior to placebo in inducing clinical remission at Week 12 in patients with moderate to severe ulcerative colitis (UC)

Clinical remission is defined as achieving a rectal bleeding Mayo subscore of 0, stool frequency Mayo subscore of 0 or 1 (with 1 point decrease from baseline) and Mayo endoscopic subscore of 0 or 1.

The rates of clinical remission and non-remission will be summarized by treatment group and by the stratification factor, previous biologic use (yes/no). See section 6.1 for details on the methods to be used to test the differences between each active treatment arm and placebo.

Ninety five percent confidence interval for the difference in proportions (LY arm – placebo) for each pairwise comparison will be obtained. If the lower limit of the 95% confidence limit is greater than zero, then that arm will be considered to be superior to placebo.

A multiple testing procedure will be utilized for the primary outcome and is detailed in section 6.6.

See section 6.4.1 for details on NRI.

6.11.2. Additional Analyses of the Primary Outcome

6.11.3. Additional analysis of the clinical remission rate at Week 12 will also be performed as per the methodology described in section 6.1. Analyses of the Secondary Efficacy Outcomes

In the analysis of secondary efficacy outcomes, no adjustments for multiple testing will be performed unless otherwise specified.

6.11.3.1. Secondary Efficacy Outcomes for the Induction Dosing Period

There are two secondary efficacy outcomes for the induction dosing period:

- 1) The proportion of patients with clinical response at Week 12.
- 2) The proportion of patients with endoscopic remission at Week 12.

The clinical response is defined as achieving at Week 12 a decrease in the 9-point Mayo subscores (comprising the subscores of rectal bleeding, stool frequency and the endoscopic findings) inclusive of ≥ 2 points and $\geq 35\%$ from baseline with either a decrease of rectal bleeding subscore of ≥ 1 or rectal bleeding subscore of 0 or 1.

Endoscopic remission is defined as achieving a Mayo endoscopic score of 0 at Week 12.

Analyses will be performed as per the methodology described in section 6.1.

The ITT population will be used for the secondary efficacy outcome analyses.

6.11.4. Secondary Efficacy Endpoints for the Maintenance Dosing Period

The following table defines the secondary efficacy endpoint evaluations performed for the Maintenance Period:

Table 3 Secondary Efficacy Endpoints for the Maintenance Period

Clinical Remission at Week 52	Achieving the following Mayo subscores at Week 52: a rectal bleeding subscore of 0, stool frequency subscore of 0 or 1 (with 1 point decrease from baseline), and endoscopy subscore of 0 or 1.
Durability of clinical remission at Week 52	Clinical remission at Week 52 for those who had clinical remission at Week 12.
Clinical Response at Week 52	Achieving at Week 52 a decrease in the 9-point Mayo subscores (comprising the subscores of rectal bleeding, stool frequency and the endoscopic findings) inclusive of ≥ 2 points and $\geq 35\%$ from baseline with either

	a decrease of rectal bleeding subscore of ≥ 1 or rectal bleeding subscore of 0 or 1.
Durability of clinical response at Week 52	Clinical response at Week 52 for those who had clinical response at Week 12.
Endoscopic remission at Week 52	Achieving a Mayo endoscopic subscore of 0 at Week 52.
Durability of endoscopic remission at Week 52	Endoscopic remission at Week 52 for those who had endoscopic remission at week 12.

Analyses will be performed as per the methodology described in section 6.1.

6.11.5. Exploratory Efficacy Endpoints

There are three exploratory efficacy endpoints:

1. To assess the change from baseline in Ulcerative Colitis Endoscopic Index of Severity (UCEIS) [4] (completed by central reader only) scores at Weeks 12 and 52.
2. To assess the change from baseline in the partial Mayo score (PGA + Stool Frequency + Rectal Bleeding) at various times during induction and maintenance.
3. To explore the effect of additional (unblinded) dosing on clinical response in patients who do not meet responder criteria at Week 12.

Summary tables for the change from baseline in UCEIS score at weeks 12 and 52 will be presented by treatment groups. The mean and 95% CIs will be presented. The change from baseline will be presented by treatment groups graphically.

Summary tables for the partial Mayo score at assessed time points and the change from the baseline assessments will be presented by treatment groups. The change from baseline will be presented by treatment groups graphically. Subscores will also be summarized separately.

Summary tables of clinical response, clinical remission and endoscopic remission for the patients who were originally randomized to LY3074828 and entered the Extension Period will be generated. Clinical efficacy findings at assessed time points and the change from the baseline assessments will be presented by original Induction Period treatment groups.

In addition to the protocol defined endpoints, additional sensitivity analyses may be performed if deemed appropriate. Additional analyses include:

- Full Mayo Endpoints:
 - Full Mayo Clinical Remission defined as a complete 12 point mayo score of ≤ 2 points and no individual subscore > 1 point (Evaluated at week 12, 52)
 - Full Mayo Clinical Response defined as a reduction in complete 12 point mayo score of ≥ 3 points and $\geq 30\%$ from baseline with an accompanying decrease in

Rectal Bleeding Score of ≥ 1 point OR an Rectal Bleeding Score of ≤ 1
(Evaluated at week 12, 52)

- Partial Mayo Endpoints:
 - Partial Mayo Response (9 point, no Endoscopy): defined as a decrease of ≥ 3 points from baseline
 - Alternate Partial Mayo Response 1 (9 point, no Endoscopy): defined as a decrease of ≥ 2 points and $\geq 25\%$ decrease from baseline with an accompanying decrease in Rectal Bleeding Score of ≥ 1 point OR an Rectal Bleeding Score of ≤ 1
 - Alternate Partial Mayo Response 2 (9 point, no Endoscopy) : defined as a decrease of ≥ 2 points and $\geq 30\%$ decrease from baseline with an accompanying decrease in Rectal Bleeding Score of ≥ 1 point OR an Rectal Bleeding Score of ≤ 1
- Symptomatic Endpoints:
 - Symptomatic Remission (RBS, SF): defined as a SF score of 0 or 1, and a RB score of 0
 - Symptomatic Response (RBS, SF): defined as a decrease of 2 points or greater from baseline
 - Change from baseline in Symptomatic Mayo (SF + RBS) Subscore
- Endoscopic endpoints:
 - Endoscopic Response (evaluated at week 12, 52): defined as at least a 1 point decrease in the endoscopic findings subscore from baseline
 - Endoscopic Healing (evaluated at week 12, 52): defined as achieving an endoscopic findings subscore of 0 or 1
- Time to Event Analyses:
 - Time to Partial Mayo Response (defined below)
 - Time to Symptomatic Response (defined below)
 - Duration of Response in Maintenance (defined below)
- Other Endpoints:
 - Alternate Modified Mayo Remission (9 point, no PGA): a rectal bleeding subscore of 0, stool frequency subscore of 0 or 1 (and no worse than baseline), and an endoscopy subscore of 0 or 1.
 - Alternate Modified Mayo Response (9 point, no PGA): defined as a Modified Mayo score decrease of ≥ 2 points and $\geq 30\%$ decrease from baseline with an accompanying decrease in Rectal Bleeding Score of ≥ 1 point OR an Rectal Bleeding Score of ≤ 1

Partial and Symptomatic analyses will be performed at every visit where collected. Analysis on endpoints including an endoscopic component will only be performed at post baseline visits where an endoscopy was performed (Week 12, Week E12, and Week 52).

Time to Response

Time to response for a given scoring method is defined (in weeks) as:

$$(First\ study\ day\ when\ response\ status\ is\ changed\ to\ "Yes" - Randomization\ date + 1) / 7$$

If a patient has not experienced response by completion or early discontinuation of induction period, the patient will be censored at the date of their last visit during the induction period.

For placebo patients continuing to the extension period, their time to response is defined as:

(First study day when response status is changed to “Yes” – Extension Period Randomization date + 1) / 7

Time to response will be evaluated during the induction and extension periods only.

Duration of Response in Maintenance

The duration of response in maintenance is defined (in weeks) as:

(study day of discontinuation or becoming eligible for rescue - Study day of randomization into Maintenance (or first dose date in Extension Maintenance) + 1) / 7

Patients who discontinue early (without loss of response) or complete the study period will be censored. Patients who have a reason for study discontinuation of lack of efficacy or Adverse event will be considered as events.

Duration of response in maintenance will be evaluated during the maintenance and extension maintenance periods only.

Histologic Remission

For the exploratory definitions of histologic remission, analyses will include the presentation of data using spotfire or any other custom analyses deemed appropriate. These presentations are for exploratory purposes only and will be presented in a manner analogous to the proposed histologic remission, described in section 6.14.9.

6.12. Health Outcomes/Quality-of-Life Analyses

6.12.1. Secondary Health Outcomes Endpoints

There are four self-administered questionnaires used for measuring health outcome in this trial:

1. PGI-S (Patient’s Global Impressions of Severity score)
2. PGI-I (Patient’s Global Impressions of Improvement score)
3. IBDQ (Inflammatory Bowel Disease Questionnaire score)
4. SF36 (36-Item Short Form Health Survey score)

Where appropriate, the total scores and sub-totals for individual dimensions collected will be summarized with means and 95% CIs by time point and by treatment group. The summary table will also include the change from baseline scores wherever applicable. The mean raw scores and mean change from baseline scores with corresponding 95% CIs will be presented graphically by treatment group and in a longitudinal fashion.

The ITT population will be used for all health outcome analyses

Mean change from baseline will be summarized by treatment group.

6.12.1.1. SF36 (36-Item Short Form Health Survey score)

Summaries of domain and summary scores will be provided by visit and change from baseline to postbaseline visits.

An ANCOVA model will be used to analyze the change from baseline in the physical component score (PCS) and the mental component score (MCS) through Week 24. The ANCOVA model will include treatment, geographic region, and prior biologic experience (prior biologic experience vs prior biologic naïve), and baseline value (consistent with adjustments of other efficacy analysis) as fixed effects and baseline score as a covariate with change from baseline as the dependent variable. To test the treatment difference between LY3074828 and placebo, the LS mean difference, 95% CI, and p-value will be presented. The LOCF approach will be used to impute missing data.

Analyses will be repeated for the eight health domains (physical functioning, bodily pain, role limitations due to physical problems, role limitations due to emotional problems, general health perceptions, mental health, social function, and vitality).

Summary statistics per treatment group will be tabulated for the transformed scale scores (physical functioning, role limitations / physical health, bodily pain, general health perceptions, vitality, social functioning, role limitations / emotional, mental health) and the two summary scores (PCS and MCS).

Minimum Clinically Important Differences (MCID):

The summary and analyses of the SF-36v2 Acute Score will include the number of patients achieving a MCID, which is defined for each summary score, physical component score (PCS) and the mental component score (MCS), as:

- MCID \geq at least 2.5 or 5-point improvement (decrease) in PCS
- MCID \geq at least 2.5 or 5-point improvement (decrease) in MCS.

The proportion of patients achieving the SF-36v2 score MCID will also be analyzed using a logistic regression model with treatment, geographic region, and prior biologic experience (prior biologic experience vs prior biologic naïve), and visit (when appropriate) as fixed effects. The p-value and 95% CI of the odds ratio from the logistic regression model will be reported. The 95% CI of the MCID rate difference will be calculated using the Newcombe-Wilson method without continuity correction. The NRI method described in Section 6.4.1 will be used to impute missing data.

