SF-36: The SF-36 is a 36-item subject-completed measure designed to be a short, multipurpose assessment of health in the areas of physical functioning, role-physical, role-emotional, bodily pain, vitality, social functioning, mental health, and general health (Ware and Sherbourne 1992; Ware et al. 1993; McHorney et al. 1994). The 2 overarching domains of mental well-being and physical well-being are captured by the mental and physical component summary scores. Responses are graded on Likert scales of varying lengths/points. The summary scores range from 0 to 100; higher scores indicate better levels of function and/or better health.

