6.1. General Considerations

Eli Lilly and Co. will be responsible for conducting the statistical analysis and for the generation, validation and final production of the Efficacy and Health Outcomes tables, figures and listings (TFLs) proposed in this document. Robarts Clinical Trials, a clinical research organization, will be responsible for conducting the statistical analysis and for the generation, validation and final production of all other tables, figures and listings (TFLs) proposed in this document.

Any change to the data analysis methods described in the protocol will require an amendment ONLY if it changes a principal feature of the protocol. Any other change to the data analysis methods described in the protocol and the justification for making the change will be described in the clinical study report. Additional exploratory analyses of the data will be conducted as deemed appropriate.

Continuous data will be summarized in terms of the number of observations, mean, standard deviation (SD), median, minimum, and maximum. The minimum and maximum will be reported to the same number of decimal places as the raw data recorded in the database. The mean and median will be reported to one more decimal place than the raw data recorded in the database. The SD will be reported to two more decimal places than the raw data recorded in the database. In general, the maximum number of decimal places reported shall be four for any summary statistic.

Categorical data will be summarized in terms of the number of patients providing data at the relevant time point (n), frequency counts and percentages. Percentages will be presented to one decimal place. Percentages will be calculated using n (the number of observations with non-missing values) as the denominator.

Change from baseline will be calculated as the visit value of interest minus the baseline value. If all baseline values are missing for a particular variable, then the change from baseline and percent change (or percent improvement) from baseline will not be calculated.

All confidence intervals (CIs) and statistical tests will be two-sided unless otherwise specified. P-values which are greater than or equal to 0.001, and less than or equal to 0.999, will be presented to three decimal places. All other p-values which are less than 0.001 will be presented as '<0.001', while p-values greater than 0.999 will be presented as '>0.999'. CIs will be presented to one more decimal place than the raw data.

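### SF-36 responder rule runs the wrong way: the SAP equates improvement with a decrease in PCS and MCS, although higher scores mean better health

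*SAP*

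**What the plan says.** SAP section 6.12.1.1 introduces a responder analysis for the SF-36. The summary "will include the number of patients achieving a MCID, which is defined for each summary score", and two bullets then set the rule. For the physical component score (PCS) it is "at least 2.5 or 5-point improvement (decrease) in PCS"; for the mental component score (MCS) it is "at least 2.5 or 5-point improvement (decrease) in MCS".

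The rule is used for inference as well as for counting: "The proportion of patients achieving the SF-36v2 score MCID will also be analyzed using a logistic regression model". An odds ratio with confidence interval and p-value follows, together with a Newcombe-Wilson interval for the rate difference. For missing values, "The NRI method described in Section 6.4.1 will be used to impute missing data".

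Two other places fix the direction of the scale. Protocol section 10.2 says that mental and physical well-being are "captured by the mental and physical component summary scores", and continues: "The summary scores range from 0 to 100; higher scores indicate better levels of function and/or better health". SAP section 6.1 sets the sign convention: "Change from baseline will be calculated as the visit value of interest minus the baseline value".

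**The concern.** On a scale where higher is better, a fall is a loss of health. The SAP rule names improvement but identifies it with a fall, and it does so for both component scores. The word in parentheses is the only explicit direction in the rule. If it is programmed, patients who clinically worsen are counted as having achieved the minimum clinically important difference (MCID), and patients who improve are counted as failures.

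SF-36 is one of the instruments named in the secondary objective on health outcomes. An effective drug produces fewer worsened patients than placebo, so it would show a lower responder rate and an odds ratio below 1 in this analysis.

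The imputation rule makes matters worse. Counting a missing patient as a non-achiever is conservative when the event is improvement. When the event is in fact worsening, the same rule counts dropouts as patients who did not worsen.

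**Working it through.** **Direction.** The plan states no figure for this analysis, so there is nothing to reproduce. The check sets three statements side by side.

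1. Higher PCS and MCS mean better health (Protocol 10.2).
2. Change = visit value − baseline value (SAP 6.1), so a decrease is a negative change.
3. An MCID responder has a decrease of at least 2.5 or 5 points (SAP 6.12.1.1).

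Take two hypothetical patients:

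| Patient | Baseline | Visit | Change | Health (Protocol 10.2) | Meets the decrease rule at 5 points? |
|---|---|---|---|---|---|
| A | 40 | 45 | +5 | better | no |
| B | 45 | 40 | −5 | worse | yes |

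Nothing in the SAP reverse-scores the SF-36. SAP section 6.18, which lists departures from the protocol analysis, mentions no change of scale and says there are no further changes.

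**Size (illustration only).** The documents give no SF-36 means or SDs, so these are assumptions. Let change be normal with mean m and standard deviation s, and let t be the threshold.

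- Increase rule: P(change ≥ t) = 1 − Φ((t − m)/s)
- Decrease rule: P(change ≤ −t) = Φ((−t − m)/s)

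With m = +5 on LY3074828, m = +2 on placebo and s = 8:

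| Threshold | Rule | LY3074828 | Placebo | Difference |
|---|---|---|---|---|
| 2.5 | increase | 1 − Φ(−0.3125) = 62.3% | 1 − Φ(0.0625) = 47.5% | +14.8 points |
| 2.5 | decrease | Φ(−0.9375) = 17.4% | Φ(−0.5625) = 28.7% | −11.3 points |
| 5 | increase | 1 − Φ(0) = 50.0% | 1 − Φ(0.375) = 35.4% | +14.6 points |
| 5 | decrease | Φ(−1.25) = 10.6% | Φ(−0.875) = 19.1% | −8.5 points |

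**Range.** With other assumed means (+6 active, +3 placebo) and SD from 6 to 10, the odds ratios for active versus placebo are:

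| Threshold | Rule | SD 6 | SD 8 | SD 10 |
|---|---|---|---|---|
| 2.5 | increase | 2.25 | 1.83 | 1.62 |
| 2.5 | decrease | 0.39 | 0.52 | 0.60 |
| 5 | increase | 2.23 | 1.82 | 1.62 |
| 5 | decrease | 0.34 | 0.49 | 0.58 |

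The estimate falls on opposite sides of 1 in every scenario.

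**Effect of the imputation.** If a fraction d of an arm is missing, unrelated to outcome, and counted as not achieving, the rate in that arm is multiplied by (1 − d). With equal d in both arms the differences shrink by that factor and keep their sign. With unequal d, the 2.5-point decrease rule in the first illustration would stop pointing against the drug only if retention on placebo fell below 0.174/0.287 = 0.61 of retention on LY3074828.

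**The case against.** The strongest reply is that the rule contradicts itself rather than being cleanly reversed. It also says improvement, and a programmer who follows that word and knows the scale would code an increase. The documents include no programming specification to show which reading was used. This stands: the misreporting is conditional on the parenthesis being followed. It does not rescue the text. Direction cannot be left to inference when the four questionnaires do not run the same way: on Protocol 10.2, lower is better for PGI-S and PGI-I, higher for IBDQ and SF-36.

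A second reply is that the reach is narrow, and that also stands. The protocol plans only mean change for SF-36 (section 12.2.6.3). The ANCOVA on PCS and MCS change, the domain analyses and the descriptive summaries in SAP 6.12.1.1 keep the right direction, and a reversed responder table beside them would probably be noticed. SF-36 is outside the multiplicity procedure of SAP 6.6, which covers only Week 12 clinical remission.

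Third, the percentages rest on assumed means and SDs, and the rates shown are before imputation. That is correct. They indicate what a reversal could do; they do not predict the trial's result.

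**Conclusion.** The rule is wrong as written. For both PCS and MCS the only explicit direction contradicts the scale defined in the protocol, and no other text in either document corrects it. This finding rests on the documents alone.

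If the parenthesis is programmed, the reported effect changes sign in every scenario examined. At 2.5 points, for instance, a 14.8-point advantage becomes an 11.3-point disadvantage under assumed mean changes of +5 and +2 with SD 8. Those sizes depend on the assumed means and SDs.

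The damage is limited to the SF-36 MCID counts, their logistic regression and the rate-difference interval. Within that scope the rule can reverse the conclusion on a secondary health outcome, so it must be corrected before those results are reported.

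**What to change.** In SAP section 6.12.1.1, define the MCID for PCS and for MCS as an increase from baseline of at least 2.5 points, and give the 5-point increase as a second, separately labelled threshold. The present wording does not say whether the two cut-offs are alternatives or two analyses, and nothing in the documents ranks them, so the sponsor should state which is intended as the main one. Remove the duplicated inequality (the ≥ sign followed by the same condition in words).

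Then check the derivation program and any SF-36 responder output already produced against the corrected rule, and rerun it if the decrease was coded.

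The revision history in SAP section 3 shows that the SF-36 analysis details were added in version 3.0, which was approved after unblinding. The correction should therefore be dated and explained in the SAP history and in the clinical study report as the repair of a direction error, so that it is not read as a responder rule chosen with results in view.

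The cost is one changed word in each of two bullets, a clarification of the thresholds, a programming check and a short note. No new data are needed.
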